9. RESEARCH DESIGN AND METHODS

The treatment duration for the study will begin 0-7 days of life and continue until 40 weeks adjusted age (full-term). Intravenous treatment will start in the first few days of life and will continue until the infant can tolerate enteral nutrition. Once enteral feeds can be started, supplementation by mouth will begin until 40 weeks adjusted age.

Laboratory blood draws:

Prior to enrollment: In addition to routine tests, blood will be tested for AST and ALT. If these tests are interpreted as abnormal, the infant will not be considered for enrollment in the study as it will be deemed a contraindication to supplemental Omegaven.

While the infant is growing in the hospital, the doctors will need to check the infant's blood to make sure the infant is developing as expected.

If the infant is enrolled in the study, the infant will be randomized in blocks of 4 by gestational age to one of two groups. The control group will get standard of care nutrition, and the experimental group will get standard of care nutrition with supplemental omega-3 fatty acids. Soon after birth, most premature infants need additional nutrition through the vein (intravenous). For the control group, there will be no changes to the standard of care parenteral nutrition. For the experimental group, the infant will receive Omegaven, an intravenous lipid preparation prepared from highly refined fish oil, in addition to the standard of care parenteral nutrition. In the instance that twins are enrolled in the study, the siblings will be randomized as one to receive the same treatment per request and approval from [name].

Transition – For the second/interventional group, Omegaven will be stopped once enteral feeds are at 120 ml/kg and enteral Oil will be started. There will be no overlap of parenteral and enteral n-3 supplementation.

If the infant can start using his/her own stomach for digestion, he/she will get fatty acid supplementation. In the control group, the infant will receive standard of care feeding. If the infant is in the experimental group, the infant will get one fourth (1/4) teaspoon per kilogram per day ($1.25\text{mL/kg/day} = 400\text{ mg omega3 per kg of fish oil per day}$) of Carlson's fish oil oral solution. Dose will be divided to at least twice a day dosing for better tolerance.

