Fatty acid supplementation will continue until the baby is full term (40 adjusted weeks of age). If the infant is discharged before he/she is full-term, the infant will be sent home with a bottle of the fatty acid oral solution for the infant to continue daily until he/she is full-term (40 weeks of age). The infant's nutritional needs will be carefully monitored by his/her doctor and nutritionist per NICU protocols.

To monitor the amount of fatty acid nutrition getting into the blood, we will check the infant's blood. As much as possible, we will coordinate the study blood collection at the same time as the routine NICU blood draws. We will collect 1.3 milliliters of blood at 4 different times spread apart while the infant is in the hospital. At each time point, we will collect about 1/4 teaspoon of blood, for a total of about 1 teaspoonful.

The blood draws will occur as the following four time points:

- Blood draw T0= Prior to parenteral nutrition, within 1st 3 days of life. This blood collection should be

taken from cord blood. If cord blood is not available, sample will be collected from a UAC, UVC, or peripheral blood draw concurrent with SOC.

- Blood draw T1= 5 days after parenteral nutrition is started; grace period +/-3 days therefore total 2-8 days after parenteral nutrition started.
- Blood draw T2= 5 days after enteral nutrition full feeds have arrived; grace period +/-3 days therefore total 2-8 days after full enteral nutrition arrived.
- Blood draw T3= Prior to discharge from hospital coinciding with time that ROP may be present, ≥ 35 weeks adjusted age.

This blood will be used for looking at what new genes (mRNA) the infant is making and to check how many and what kind of fatty acids the infant has in the blood. Before testing, the blood will be stored in a storage facility at the UCSD Department of Ophthalmology Blood Bank and labelled with a barcode without the infants' personal information. This is not the infant's DNA, and no DNA will be isolated or tested. Samples will be stored for 10 years. After this time point, all samples will be destroyed if not used by that time. If the parent decides to withdraw consent the blood samples that were already drawn will be destroyed, however, any previously obtained data from sample testing will be kept.

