Our primary analytic approach will use generalized linear mixed models (GLMM). These methods will address problems of missing data, variable timing of the subject visits, and other possible unintended violations of design. Although our retention and follow-up plan is designed to minimize missing data, an advantage of the GLM models is that they allow us to maximize statistical power by not excluding subjects with some missing data. More specifically, GLM assumes that the data can be missing at random (MAR) or missing completely at random (MCAR). The benefit of this assumption is with a repeated measure problem (e.g., longitudinal data) you can still analyze data from all subjects, even if some have missing data (assumed MAR or MCAR). Mixed regressions will also allow us to estimate an intercept and slope for each patient based on all available data for that individual augmented by the data from the entire sample, with two random effects being used to model time trends (i.e., a random intercept and a linear trend). Further details of selected analyses related to each outcome are provided next.

For Outcome (a-b), the primary outcome is DHA at a specified period of time (i.e. 40 weeks) to assess the basic fatty acids. Outcome (a) posits that patients in Group 1 will differ from those in Group 2 with respect to i) DHA

ii) EPA iii) AA iv) bioactive metabolites. To assess Outcome (a) (i.e. to evaluate the effects of group, time, and their interaction on the change from baseline DHA measurements), a mixed effects model with group (IV Omegaven then PO baby fish oil or Intralipid), time, and group by time interaction as fixed effects, and random intercept and slope to account for within subject correlation. We expect that the interaction in question will be significant.

For Outcome (c), we hypothesize that Group 1 and Group 2 will have a different severity stage of ROP. To assess Outcome (c), we will use a *Mixed-effects ordinal logistic regression model* with severity stage of ROP after 40 weeks (Stage I, II, III, IV, V) as the outcome variable. The same fixed and random effects mentioned above will be used in evaluating Outcome(c).

All statistical analyses will be performed using SAS software version 9.3 (SAS Institute, Cary, North Carolina, USA).

[figure not shown]
Power Calculations

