The power calculations that follow were conducted using the software PASS and are based on two-sided tests, with a 0.05 type I error rate. A sample size N=40 was assumed. Power calculation for the primary outcome is presented below.

Power for Outcome (a)

Outcome (a) tests the effect that Group 1 has a different average DHA measurement compared to Group 2. The power calculation for Outcome (a) was based on a two-sided two-sample t-test with a dependent continuous variable (i.e. pre-post difference in DHA measurements) on a categorical independent variable (i.e. Group 1 and Group 2) with a sample size of 40 total subjects. These subjects were equally distributed between each of the two treatment groups. In Pawlik et al. (2013), the mean pre-post difference were 42 $\mu\text{mol/L}$ for patients in Group 1 and 27 $\mu\text{mol/L}$ for patients in Group 2. Following Pawlik et al.'s sampling distribution, we also considered 6 common standard deviation estimates for the power calculation 5, 7, 9, 11, 13, and 15. It should be noted that as the common standard deviation within the group decreases, the group will yield greater power to detect an intervention group effect. As illustrated by the curve in Figure 1, we will have over 80% power to detect a mean difference among the 2 groups of average DHA measurements with a common standard deviation of 15, which is the smallest difference that we can detect with the proposed sample size.

Figure 1: Power for Group Effect on the DHA at 40 weeks.

Note: Even though the data analysis plan relies on longitudinal methods (GLMM), due to unavailability of estimates for repeated measures, the above power calculations were based on a single time point method (two sample t-test). However, the use of a longitudinal method generally results in an increase in power, therefore we believe we will retain sufficient power for the study based on the methods proposed here.

In addition, we have determined that in order to reach a targeted sample size of 40 subjects completing treatment, we will need approximately 60 subjects enrolled to this protocol. This is our target accrual.

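### Allocation is blocked by gestational age and keeps twins together, but neither feature is in the DHA or ROP model; if they act on DHA change, the group-by-time test departs from 5%, and the documents cannot settle the net direction.

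*Combined protocol and SAP*

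**What the plan says.** All of this is in section 9, Research Design and Methods, of the combined protocol and SAP.

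- **Blocking.** An enrolled infant is allocated as follows: "the infant will be randomized in blocks of 4 by gestational age to one of two groups". The gestational-age bands are not given.
- **Siblings.** The rule is "twins are enrolled in the study, the siblings will be randomized as one to receive the same treatment per request and approval from", with a removed name after it. No expected number of twins is given.
- **DHA model (Statistical Analysis).** The terms are group, "time, and group by time interaction as fixed effects, and random intercept and slope to account for within subject correlation". On the interaction the plan adds: "We expect that the interaction in question will be significant".
- **ROP model.** For ROP stage the plan says "The same fixed and random effects mentioned above will be used in evaluating Outcome(c").
- **Power Calculations.** The basis is a two-sample t-test "with a sample size of 40 total subjects", 20 per group, which treats infants as independent.

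Nothing else in the document adds a gestational-age covariate, a family term or a clustered variance.

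**The concern.** An analysis should reflect how the units were allocated. Here two features of the allocation have no counterpart in the model, and they pull in opposite directions.

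- **Siblings.** A twin pair kept together is a cluster of two. If the pair's DHA trajectories are alike, the planned standard error is too small.
- **Gestational age.** Blocking balances it between arms. If it predicts DHA change but is left out, its contribution stays in the residual. The standard error is then too large and power is lost.

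The protocol anticipates twins, since it has a rule for them. It also ties gestational age to exposure and timing. Treatment "will begin 0-7 days of life and continue until 40 weeks adjusted age (full-term"), so it lasts 40 - 23 = 17 weeks, less up to one for the start day, for birth at 23 weeks, and 40 - 30 = 10, less up to one, for birth at 30 weeks. The last blood draw, T3, is at or after "35 weeks adjusted age": at least 35 - 23 = 12 weeks against 35 - 30 = 5 weeks after birth. A relation between gestational age and DHA change is therefore plausible, though not shown.

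What is at stake is how to read a p-value near 0.05 for the effect the plan expects to be significant. Choosing these terms after seeing the data would be open to challenge.

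**Working it through.** **1. The plan's own power figure.** Inputs from Power Calculations: 20 per arm, mean changes 42 and 27 (difference 15), SD up to 15, two-sided 0.05. Noncentrality = (15/15) x sqrt(20/2) = 3.16 on 38 df, giving 86.9% (94.5% at SD 13). The claim of more than 80% is reproduced for independent infants.

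**2. Quantities the documents do not give (assumed).** f = share of infants in twin pairs, 0 to 0.4. ICC = within-pair correlation of the DHA slope, including any part due to gestational age, 0.2 to 0.8. R2 = share of slope variance explained by gestational age, 0 to 0.2. Two gestational-age strata.

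**3. Formula.** With complete, balanced visits, the linear group-by-time test compares mean per-infant slopes between arms. The true variance of that comparison, relative to what the planned model assumes, is

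V = (1 - R2) + f x max(ICC - R2, 0),

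and the large-sample type I error is 2 x [1 - Phi(1.96/sqrt(V))]. For example, f = 0.2, ICC = 0.5, R2 = 0.2 gives V = 0.8 + 0.2 x 0.3 = 0.86, hence 3.5%.

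**4. Results for the planned test (type I error, %).** Simulation A: 40 infants, no loss, 20,000 runs. Simulation B: 60 enrolled, families allocated in blocks of 4 within two strata, 20 infants lost at random, 40 analysed, 40,000 runs. A dash means no result is reported here.

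| f, ICC, R2 | V | Formula | A | B |
|---|---|---|---|---|
| 0, -, 0 | 1.00 | 5.0 | 5.0 | 5.0 |
| 0, -, 0.1 | 0.90 | 3.9 | 4.0 | 4.3 |
| 0, -, 0.2 | 0.80 | 2.8 | 3.1 | 3.7 |
| 0.2, 0.5, 0 | 1.10 | 6.2 | 6.2 | 5.9* |
| 0.3, 0.8, 0 | 1.24 | 7.8 | 8.2 | - |
| 0.4, 0.8, 0 | 1.32 | 8.8 | - | 7.8 |
| 0.2, 0.5, 0.1 | 0.98 | 4.8 | 5.0 | - |
| 0.2, 0.5, 0.2 | 0.86 | 3.5 | 3.9 | 4.1 |
| 0.4, 0.8, 0.1 | 1.18 | 7.1 | - | 6.4 |

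*8,000 runs.

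Over the full grid of 39 points, simulation B gives 3.6% to 7.8%.

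**5. Level effects only.** When twin correlation and gestational age act on DHA level and not on slope, the infant random intercept absorbs them and the test stays at 4.9-5.0%. For the same reason, adding only a gestational-age main effect and a family intercept changes nothing. In REML runs of 2,500 trials, planned and modified tests both gave 3.2%, 6.4% and 7.3% at (0.2, 0.5, 0.2), (0.4, 0.8, 0.1) and (0.4, 0.8, 0).

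**6. Analysing as randomised.** With f 0.2-0.4, ICC 0.5-0.8 and R2 0.1-0.2 in simulation B, the planned test gives 4.1-6.4%, gestational age by time alone 5.4-7.5%, clustering alone 3.3-4.6%, and both together 4.9-5.3% (4.9-5.4% over all 39 points). Both parts are needed.

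**7. Power with twins.** For the t-test, effective n per arm = 20/(1 + f x ICC). For (f, ICC): (0.2, 0.5) gives 18.2 and 83.4%; (0.3, 0.5) gives 17.4 and 81.6%; (0.3, 0.8) gives 16.1 and 78.5%; (0.4, 0.8) gives 15.2 and 75.7%.

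**The case against.** The strongest reply is that the effect is small, rests wholly on assumed inputs, and may be nil.

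- **Timing is not slope.** Longer follow-up for the most preterm infants does not itself mean a different rate of DHA change. The plan says its mixed models handle variable visit timing, and if time is entered as actual time, differing T3 dates are covered. Supplementation can also continue after T3. This stands: the timing argument makes a slope effect plausible and no more.
- **The number of strata matters.** With eight weekly strata instead of two, and no twins, the planned test gives 4.6% and 4.0% at R2 of 0.1 and 0.2, nearer nominal. Stratum indicators would then cost about 3 points of power when gestational age has no effect. This stands and shapes the fix.
- **The simulations are simplified.** They assume complete, equally spaced visits and loss at random across arms. The real draws are unequally spaced, partial data are kept, and the withdrawal rule for interrupted study drug applies only to the Omegaven arm. The decimals should not be over-read.
- **The twin wording is ambiguous.** The reference to request and approval might mean that co-allocation is optional, or that the rule itself was approved. The point does not depend on which.

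A reader might infer that the test is off 5% in an unknown direction as soon as twins enrol or gestational age predicts outcome. The documents do not support that. Each cause alone has a known direction, neither matters unless it acts on DHA change, and only the net of the two is unsigned.

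**Conclusion.** The mismatch stands: two stated features of the randomisation are missing from fully listed DHA and ROP models. For DHA, sibling correlation in change makes the group-by-time test liberal, a gestational-age effect on change makes it conservative, and the net sign cannot be found from the documents. With two strata and the assumed ranges above, type I error is roughly 3.5-8%, and some combinations give about 5%. The twin share, ICC, R2 and strata are all assumptions, so confidence in the size is moderate. It should be corrected before analysis, but it does not undermine the trial.

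Two further inferences go too far. The power statement is not wrong as made: it holds for independent infants, and falls below 80% only with heavy twinning and high sibling correlation. For the ROP model the omission is clear, but no error rate was established and none is claimed.

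**What to change.** - **DHA model.** Add gestational age at birth in weeks (linear), or the randomisation stratum if there are only a few bands, together with its interaction with time. Use family-clustered variance with a small-sample correction (CR2 with Satterthwaite degrees of freedom), each singleton being its own family.
- **ROP model.** Add gestational age in weeks as a fixed effect and use family-clustered variance.
- **Reporting and data.** State the gestational-age bands used for blocking, and record a sibling-set ID.

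A random sibling intercept and slope should not be the main method. In the REML runs with gestational age by time it gave 4.7-6.6%, including 6.3% where the planned test gave 6.4%, and the sibling slope variance was estimated at zero in 4-32% of trials. CR2 was checked on per-infant slopes, not in the full mixed model, so its implementation in the planned software should be confirmed.

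**Cost.** This needs SAP wording and one derived column. Gestational age is already needed for eligibility and blocking, and section 11 (Recruitment) lists birth date, address and name among the identifiers that may be used, so siblings can be linked. If gestational age has no effect, adding it costs about 0.4 point of power as weeks or two bands, and about 3 points as many weekly indicators. At a 1 SD difference, the largest loss for the combined fix is about 5.5 points (84.5% to 79.05% at f = 0.4, ICC = 0.8, R2 = 0), where the planned test's higher power comes with a 7.8% error rate. The largest gain is about 5.0 points (87.3% to 92.2% at f = 0.1, ICC = 0.2, R2 = 0.2).

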7. BACKGROUND AND SIGNIFICANCE

Clinical:

Approximately 517,000 infants are born prematurely every year¹, and as low birth weight and premature infants are surviving longer, they are at high risk of developing severe ROP. In the United States, 2,000 infants per year are diagnosed with severe ROP, which is the leading cause of irreversible childhood blindness in the United States. In our NICU, we care for between 60 and 80 infants each year that are born with low birth weight.

Usual parenteral nutrition protocols do not meet the infants' fetal accretion rates. Despite receiving 14-28 mg DHA/kg/day,² preterm infants have lower serum DHA and EPA levels than they would have had *in utero*, and

their tissues have lower n-3 and n-6 fatty acid than full term infants, indicating that their dietary needs are often not met.³ Preterm and small for gestational age infants have altered serum phospholipid fatty acid profiles with lower DHA and polyunsaturated omega-3 fatty acids than appropriate for gestational age infants.⁴ Low birth weight infants often have severe lung disease and are exposed to exogenous oxygen, which causes retinal blood vessel attenuation, retinal hypoxia, up regulation of pro-angiogenic factors, and neovascularization, which can lead to irreversible vision loss.

In a recent Polish prospective interventional study, Pawlik et al. showed that in preterm infants (average 28 week gestation, 935 gram birth weight), continuous intravenous n-3 fatty acids with Omegaven® from day one to day 28 of life, followed by enteral omega-3 fatty acids is safe and resulted in a significantly decreased need for ROP laser treatment. In the treatment group, 9 of 60 infants needed laser compared with 22 of 70 infants in the control group.^{7,12} On treatment, infants had higher plasma and red blood cell DHA levels at 7 and 14 days and a lower risk for cholestasis. This study showed that treatment was well tolerated in preterm infants and that Omegaven® has a positive effect on ROP pathogenesis, but no investigations were done into the mechanisms by which ROP was suppressed in the experimental group compared with the control arm. There is also no clinical data that currently differentiates the differences in the blood biology (fatty acids, gene expression, and proteins) in infants with and without severe ROP.

Translational:

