We will examine the infant's eyes according to the standard NICU guidelines and protocols. We will also examine the infant's eyes in our eye clinic after discharge over time as we do for all premature infants to support the infant's visual development.

During the study:

Maternal diet questionnaires will be administered to the maternal subjects following enrollment. This questionnaire is the Omega 3 Fatty Acid Questionnaire and has been validated in a related study for this fatty acid¹⁹. It is anticipated to take 10-15mins to complete. Mothers will be asked to complete this questionnaire at the time of enrollment.

Blood samples will be collected 4 times. When possible, and in the majority of blood draws, 1.3 cc of whole blood will be collected at the same time as other blood draws to avoid multiple sticks. Whole blood will be collected in a green or lavender top tube. One hundred μ l of plasma will be isolated, and this will be aliquoted into in two tubes and frozen (-80°C).

Lipidomics: Plasma fatty acids will be tested using a preprandial whole-blood sample (1.3 mL) drawn 2-4 hours after the parenteral nutrition (PN) had ended for the day and after enteral feedings were held for 3 hours if the patient was also fed enterally. The schedule for sampling will be as follows: prior to parenteral nutrition within ≤ 3 days of life; within 5-8 days after parenteral nutrition is started; within 5-8 days after enteral nutrition full feeds is started; and prior to discharge from hospital coinciding with time that ROP may be present. The samples will be sent to [name] of Engineering in Medicine Laboratory at UCSD or another UCSD laboratory for internal validation of assays. [name] lab (UCSD Department of Ophthalmology) or another laboratory with similar capabilities will perform some of the RNA isolation and analysis. Capillary gas chromatography/mass spectroscopy will be the one of the main methods used to determine the phospholipid profile.

Transcriptomics: From the plasma isolated from the whole blood samples, 50 μ l will be used for mRNA isolation. This will be collected and frozen as the study is ongoing. The fold expression of genes associated with the fatty acid synthesis pathway, hypoxia and pro-angiogenic pathways will be correlated with clinical disease.

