12. INFORMED CONSENT

Parents of potential subjects will be asked to provide written consent, using an IRB-approved consent form. The consent process will take place prior to performing any study related procedures and in a private location. The potential subject will already be admitted to the hospital. The Investigator or study coordinator will describe the study, including detailed information about risks and benefits, to the parents of potential subjects. The investigator or study coordinator will provide the parent with an IRB-approved consent form. Parents will be given ample time to read this consent form at the same visit or may take it with them to read at another time. Parents will be given the opportunity to ask and receive answers to all questions they may have about the study, its risks and benefits, or the consent form itself before signing the consent form. As this research is subject to HIPAA privacy rule provisions, participants will also be requested to sign a separate authorization for the use of protected health information (i.e., HIPAA form specific to the research study). The investigator or study coordinator will obtain informed consent in a language understood by the prospective participant or their legally authorized representative, using certified translations of study documents and qualified translators, where applicable.

For the follow-up eye exam data, we will obtain a signed medical release authorization form for any patients scheduled to receive an exam outside of UCSD as their SOC.

Subjects who fulfill the eligibility criteria will be offered further participation in this study. Only subjects who have consented and provided HIPAA authorization will have identifiers or linked information (e.g., subjects initials, study numbers, etc.) recorded on the Screening/Enrollment Log.

All signed consents will be maintained in marked binders, secured in locked filing cabinets within private administrative offices at UCSD's Clinical Teaching Facility on campus accessible to study coordinators and principal investigators only.

A copy of the HIPAA authorization and informed consent form(s) that will be used on this study are attached to this IRB application for your review.

Oral consent will be obtained from the maternal subjects for completion of the maternal questionnaires. No PHI will be collected from the mother nor will her medical records be accessed.

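### T0 may be cord blood or infant blood, but the plan neither records the source nor adjusts the change-from-baseline analyses for it

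*Combined protocol and SAP*

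**What the plan says.** Section 9 (Research Design and Methods) defines the first sample as "Blood draw T0= Prior to parenteral nutrition, within 1st 3 days of life". It should be "taken from cord blood"; failing that, "If cord blood is not available, sample will be collected from a UAC, UVC, or peripheral blood draw concurrent with SOC". The Lipidomics paragraph of the same section repeats the window, "prior to parenteral nutrition within ≤ 3 days of life", without naming a specimen. Its rule about sampling some hours after the day's parenteral nutrition has ended cannot apply to a sample taken before any has been given.

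Under Outcome Measures, Outcomes 1 and 2 are changes in fatty acids and in mRNA expression. Under Statistical Analysis, the model for Outcome (a) addresses "the change from baseline DHA measurements". Its fixed effects are group, time and group by time, with a random intercept and slope. No model is written out for mRNA. The power calculation also uses the pre-post difference in DHA. Nowhere is the T0 specimen source recorded, stratified on or adjusted for.

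On consent, section 12 says: "The consent process will take place prior to performing any study related procedures and in a private location". It continues: "The potential subject will already be admitted to the hospital". Section 11 likewise describes subjects as already hospitalized when they are recruited.

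**The concern.** Cord blood reflects fetal supply through the placenta. An infant sample drawn up to day 3 is taken after that supply has ended. If DHA or mRNA levels differ between the two, change from T0 means one thing in infants with a cord sample and another in the rest. The cord-to-infant step then sits inside the change score of some infants and not others, as noise unrelated to treatment. With 20 completers per arm, the share of cord baselines can also differ between arms by chance. If the source is not recorded at the time, it may be impossible to recover at analysis.

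Consent is a separate difficulty. Cord blood is obtained at delivery, while the consent text describes an infant already admitted. The plan gives no route by which its preferred specimen is consented for.

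**Working it through.** **Inputs from the plan (Power Calculations).** Mean pre-post DHA change 42 and 27 µmol/L, so the difference is 42 − 27 = 15. Common SDs considered: 5, 7, 9, 11, 13 and 15. N = 40, 20 per arm, two-sided 0.05.

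**Inputs that the documents do not give (assumed).** The gap g is the mean cord-minus-infant difference in DHA: 0, 10, 15 or 20 µmol/L. The share p of infants with a cord T0 is 0.5 or 0.1.

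**Step 1: the plan's own figure.** Standard error = 15 × √(2/20) = 4.74. Noncentrality = 15/4.74 = 3.16. Two-sample t-test power on 38 degrees of freedom is 86.9% (88.5% by the normal approximation). The stated power of over 80% at SD 15 reproduces. The largest SD that keeps 80% is 16.5.

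**Step 2: effect of mixing sources.** If source shifts the change score by g and is independent of arm, total SD = √(SD² + p(1 − p)g²). For SD 15, p = 0.5 and g = 15: √(225 + 0.25 × 225) = √281.25 = 16.8. Power by the same t-test:

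| SD in plan | Cord share p | g = 0 | g = 10 | g = 15 | g = 20 |
|---|---|---|---|---|---|
| 15 | 0.5 | 86.9% | 83.2% | 78.7% | 72.7% |
| 15 | 0.1 | 86.9% | 85.6% | 83.9% | 81.6% |
| 13 | 0.5 | 94.5% | 91.3% | 86.9% | 80.5% |
| 11 | 0.5 | 98.7% | 96.9% | 93.5% | 87.5% |

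At SD 15 and p = 0.5, power drops below 80% once g exceeds about 13.7 µmol/L.

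**Step 3: chance imbalance.** The between-arm difference in cord share has SD √(2 × 0.25/20) = 0.158, about 16 percentage points. With g = 15 this moves the treatment estimate by 0.158 × 15 = 2.4 µmol/L (one SD), or 2.4/15 = 16% of the assumed effect. This is the added variance of step 2 seen from another side: 281.25 × 2/20 − 225 × 2/20 = 28.1 − 22.5 = 5.6 = 2.4². It must not be counted as a second loss.

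**Step 4: after adjustment.** With a source term in the model, the residual SD returns to 15 and the error degrees of freedom fall from 38 to 37. Power is then about 86.8%, before a small further loss if source happens to be unbalanced between arms.

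**The case against.** Four counter-arguments deserve weight.

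- **No gap is documented.** The nearest support is the statement in section 7 that "preterm infants have lower serum DHA and EPA levels than they would have had" in the womb. That sentence concerns infants already receiving DHA in their nutrition, whereas T0 comes before parenteral nutrition. It makes a difference plausible but does not compare cord blood with pre-nutrition infant blood, and nothing compares mRNA by source. This stands: neither size nor direction can be established.
- **The low-power cases stack assumptions.** They need an even mix (the worst case), the largest of six SDs, and a gap close to the whole treatment effect. If the consent sequence makes cord samples rare, the mix is far from even and the loss is small. This also stands.
- **The primary outcome is also described as DHA at 40 weeks.** A level does not depend on the T0 source. But the model and the power calculation both use change, so T0 still matters as the text is written.
- **Cord blood spares infant blood.** Demanding an infant T0 from everyone would add a 1.3 mL draw where cord blood exists, and section 14 lists anemia as a risk. Moving the baseline to any time before study lipid could also admit samples taken after standard parenteral nutrition. This stands, so a single infant-blood baseline for all is not recommended here.

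A reader might also infer that the cord sample cannot be collected at all. The documents do not go that far. Section 11 puts consent in the mother's hospital room, which does not exclude antenatal consent, and available cord blood could mean blood kept from routine care. The consent pages are not in the copy reviewed, so their silence proves nothing. What exists is a tension that needs reconciling.

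**Conclusion.** The point holds as a cheap improvement to the baseline definition. T0 has two possible sources, the written analysis uses change from T0, and source is neither recorded nor modelled.

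The cost depends on two unknowns. With an even mix and SD 15, a gap of 10 µmol/L costs 86.9 − 83.2 = 3.7 percentage points of power and a gap of 20 costs 86.9 − 72.7 = 14.2. With few cord samples, or an SD of 13 or less, the planned 80% survives every gap examined. These figures assume that source shifts the change score by a constant and is unrelated to arm.

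Two stronger readings are not supported. One is that the mixed baseline biases the treatment comparison: T0 precedes study lipid and nothing ties source to arm, so the expected harm is variance and chance imbalance only. The other is that the stated power is wrong: it reproduces, and simply makes no allowance for a source mix.

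**What to change.** 1. Keep the T0 window before parenteral nutrition. Record the specimen source (cord, UAC, UVC or peripheral) and age in hours at T0 on the case-report form.
2. Include source and the baseline value (DHA, or the relevant mRNA) as covariates in the change models, and write out the mRNA model. The baseline value alone is not enough, because the same reading may mean different things in cord and infant blood.
3. Prespecify a sensitivity analysis restricted to infants with an infant-blood T0.
4. Reconcile the preference for cord blood in section 9 with sections 11 and 12 by stating how and when consent for cord blood is obtained, including whether blood retained from delivery may be used.

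The cost is protocol and SAP wording, a small addition to the case-report form, and about one degree of freedom for the source term. The sensitivity analysis will have fewer infants and should be read as supportive. No extra blood is drawn.
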